12 APPENDIX: ADVERSE EVENTS AND SERIOUS ADVERSE EVENTS – DEFINITIONS, SEVERITY, AND CAUSALITY

12.1 Further Details and Clarifications on the AE Definition

An AE won't be recorded in the following circumstances: diseases or conditions or laboratory abnormalities that have been existing or detected prior to screening visit without further deterioration. No adverse medical incidents occur (e.g., hospitalization due to elective surgery, social reasons, and/or personal reason).

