2.2 Summary of Benefits and Risks

Benefits

This is a single-center, randomized, single-blind, single-dose, parallel-group trial to assess

the pharmacokinetic similarity between CHS-1420 40 mg/0.4 mL and HUMIRA® (Adalimumab) 40 mg/0.4 mL in healthy Chinese adult participants under fasting conditions. No benefits are expected for the individual participant. However, the trial data may support the registration application for a proposed biosimilar to HUMIRA® (Adalimumab), which can further provide an alternative therapeutic choice and benefit the indicated population.

Risks

CHS-1420 40 mg/0.4 mL, developed by Hong Kong King-Friend, a subsidiary corporation of Nanjing King-Friend Biochemical Pharmaceutical Co., Ltd., is designed as a biosimilar to HUMIRA® (Adalimumab). Data derived from analytical studies, animal studies indicated similarity between CHS-1420 and HUMIRA®.

For individual participant, the risks of treatment with HUMIRA® (Adalimumab) can be found in the Prescribing Information [2]:

Most common adverse reactions (>10%) during HUMIRA® (Adalimumab) treatment are: infections (e.g. upper respiratory, sinusitis), injection site reactions, headache and rash.

Other warnings and precautions for treatment with HUMIRA® (Adalimumab) are as follows:

- *Serious infections:* Do not start Adalimumab during an active infection. If an infection develops, monitor carefully, and stop Adalimumab if infection becomes serious.
- *Invasive fungal infections:* For patients who develop a systemic illness on Adalimumab, consider empiric antifungal therapy for those who reside or travel to regions where mycoses are endemic.
- *Malignancies:* Incidence of malignancies was greater in Adalimumab-treated patients than in controls.
- *Anaphylaxis or serious hypersensitivity reactions:* may occur.
- *Hepatitis B virus reactivation:* Monitor HBV carriers during and several months after therapy. If reactivation occurs, stop Adalimumab and begin anti-viral therapy.
- *Demyelinating disease:* Exacerbation or new onset, may occur.
- *Cytopenias, pancytopenia:* Advise patients to seek immediate medical attention if symptoms develop, and consider stopping Adalimumab.
- *Heart failure:* Worsening or new onset, may occur.
- *Lupus-like syndrome:* Stop Adalimumab if syndrome develops.

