5.4 Exclusion Criteria

- 1) With \geq 5 cigarettes per day on average within 3 months before screening, or not able to quit smoking during the trial;
- 2) Allergic constitution, or allergic to the drug components and its analogues; history of allergic reaction to a biological medication;
- 3) A history of alcohol abuse (alcohol consumption of more than 14 units per week : 1 unit of alcohol = 285 mL beer, or 25 mL spirits, or 100 mL wine);
- 4) Blood donation or massive blood loss ($>$ 400 mL) within 3 months before investigational products dosing; Or any blood donation plan from screening until 3 months after administration;
- 5) History of any major surgery within the past year, or history of any surgery within the past 6 months; or any elective medical procedures, including dental procedures;
- 6) Any history of organ transplantation;
- 7) Medical history of tuberculosis (or suspected tuberculosis), or with a positive tuberculosis test result;
- 8) Medical history of heart failure or other cardiac disorders which may lead to heart failure, e.g. coronary heart disease, hypertension, senile degenerative valvular disease, rheumatic valvular heart disease, dilated cardiomyopathy, acute severe myocarditis;
- 9) Medical history of immune system disorders (e.g. systemic lupus erythematosus, multiple sclerosis, *etc.*), or positive results of antinuclear antibody tests;
- 10) Medical history of recurrent or chronic infections (including transverse myelitis, optic neuritis, other demyelinating disorders, *etc.*), or a history of an opportunistic infection within the past year due to bacterial, mycobacterial, invasive fungal, viral, parasitic, or other opportunistic pathogens;
- 11) History of seizure attack;
- 12) Medication history of TNF- α blockers e.g. Adalimumab or its analogues;
- 13) Any medication of monoclonal antibodies within the past year before investigational products dosing;
- 14) Any usage history of prescription medicines or OTCs (especially antibiotics), or Chinese herbal medicine or health supplementary within 30 days before investigational products dosing;
- 15) Any vaccination within 3 months before investigational products dosing, or any plan for vaccination within 3 months after investigational products administration;

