8.3.4 Clinical Laboratory Assessments

The clinical laboratory tests, including biochemistry, hematology, urinalysis, coagulation function, serum pregnancy test (only for females), will be performed at the screening visit (the results obtained within 7 days considered acceptable), and on Day 4, Day 16, Day 30, Day 65. In addition, serum pregnancy results for females will also be confirmed before admission on Day -1. A list of clinical laboratory assessments is included in Section 13.2.

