8.4.2 Time Period and Frequency for Collecting AE and SAE Information

The nursing and medical staff will closely observe the participants for any AEs throughout the trial. Once dosed, any abnormalities of clinical significance e.g. clinical sign and symptom, vital signs, physical examination, ECG, laboratory test results in a participant will be collected as AEs or SAEs until completion of the trial.

Before leaving the research facility, the participants will be informed by the staff of the precautions and to report any AEs until completion of the trial.

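### The AE exemption is anchored at the screening visit rather than at dosing, and the SAP has no treatment-emergent rule, so conditions that begin in between are counted as AEs

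*Protocol*

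**What the plan says.** **AE baseline.** Protocol 12.1 states which conditions are not recorded as AEs: "diseases or conditions or laboratory abnormalities that have been existing or detected prior to screening visit without further deterioration". Protocol 8.4.2 sets the start of collection: "Once dosed, any abnormalities of clinical significance e.g. clinical sign and symptom, vital signs, physical examination, ECG, laboratory test results" are collected as AEs or SAEs until the trial is complete. The Schedule of Activities allows screening up to 28 days before dosing. SAP 5.6.1 repeats the AE and SAE definitions, the severity grades and the causality categories. It gives no treatment-emergent definition and no rule on onset relative to the dose. Protocol 8.4.4 requires the time of onset to be recorded for each AE.

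**Infection at entry.** In summarising the prescribing information, protocol 2.2 reports the warning "Do not start Adalimumab during an active infection". The infection-related exclusions in 5.4 are:

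- item 7: "Medical history of tuberculosis (or suspected tuberculosis), or with a positive tuberculosis test result";
- item 10: "Medical history of recurrent or chronic infections", or "a history of an opportunistic infection within the past year";
- item 19: hepatitis B, hepatitis C, HIV and syphilis.

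None of them names an acute or active infection.

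**The concern.** A safety comparison needs a single baseline, and for a single-dose trial that is the dose. Here the exemption ends at one time point (the screening visit) and collection begins at another (dosing). Whatever starts in the interval falls on the AE side by default. A minor infection that began a few days before the dose and is still present afterwards is an obvious example.

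Safety is part of the secondary objective, and protocol 2.2 lists infections first among the most common adverse reactions to the reference product. Illness that the product cannot have caused would be counted in the same table as illness that began after it. The warning in 2.2 makes the same interval relevant to eligibility, because it asks whether the person is infected at the time of dosing, not at screening.

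**Working it through.** There is no figure to reproduce; the check is a timeline read against the wording of 12.1 and 8.4.2.

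1. **Present before the screening visit and not worse.** Exempt under 12.1, so not an AE.
2. **Present before the screening visit and worse later.** The exemption is lost, so it is an AE. Because the anchor is screening, the wording does not separate worsening before the dose from worsening after it.
3. **Starts or is first detected between screening and dosing, and has gone by the time of dosing.** Not exempt, but collection under 8.4.2 has not begun.
4. **Starts or is first detected between screening and dosing, and persists unchanged after the dose.** Not exempt under 12.1 and inside collection under 8.4.2 if clinically significant. It is recorded as an AE and enters the Safety Set analysis. The window is up to 28 days.
5. **Starts after the dose.** An AE, as intended.

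Case 4 is the fault, and case 2 shares the wrong reference point.

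**Does the SAP correct this?** Not in its text. SAP 5.6.2, 5.6.4 and 5.6.5 describe change from pre-dose to post-dose for laboratory tests, vital signs and ECG, so AEs are the one safety domain without a dose-based reference. Protocol 2.2 itself describes the cited PK similarity study in terms of treatment-emergent events.

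**Is an acute infection kept out at entry?** Three general exclusions in 5.4 can do it:

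- item 14 excludes anyone who has taken medicines in the 30 days before dosing, which catches a treated infection;
- item 18 excludes clinically significant findings, as a physician judges them;
- item 27 leaves other unsuitability to the investigator.

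The first works indirectly and the other two by judgement. The checks that would inform that judgement are mostly early. Section 8.3.1 places the only full pre-dose physical examination at screening. Section 8.3.4 says the laboratory tests "will be performed at the screening visit (the results obtained within 7 days considered acceptable), and on Day 4, Day 16, Day 30, Day 65", with only a pregnancy test added on Day -1. Section 8.3.2 places vital signs at screening and then within 1 h before the dose. That last reading comes after the Day -1 eligibility review and after randomization (6.6.2). A questionnaire is completed on Day -1, but its content is not given.

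**The case against.** The defence has several good points.

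- **The entry criteria are not silent.** Items 14, 18 and 27 are mandatory exclusions. Section 7.2 also lets the investigator withdraw an enrolled participant, and 6.6.2 foresees withdrawal before treatment. An abnormal pre-dose reading could therefore still lead to withdrawal before dosing. A reader might infer that the protocol admits acutely infected participants in breach of its own rule. The documents do not support that: the sentence in 2.2 is a reported label warning, not a trial rule. What remains is that the warning has no named counterpart in 5.4, whereas heart failure, lupus, demyelinating disease and hepatitis B do.
- **Causality is protected.** A reader might infer that pre-dose illness inflates the count of drug-related AEs. Under 12.4 the three drug-related categories all require credible timing, and onset is recorded, so a known pre-dose onset argues against those categories.
- **The arms should be affected alike.** Allocation is randomized 1:1, and under 6.6.3 staff who know the allocation may not assess AEs. Conditions that began before the dose should be roughly balanced.
- **Not every minor illness counts.** Section 8.4.2 is limited to abnormalities of clinical significance, and an unchanged condition from before screening is exempt.
- **The tables are not visible.** SAP section 7 places table and listing shells in a separate document, which might split AEs by onset.

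These points limit the harm but leave the anchor in 12.1 unchanged. The rule as written uses the wrong reference time, and a split that exists only in table shells would rest on no definition in the protocol or SAP.

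**Conclusion.** The point holds as a misplaced baseline: case 4 is recorded and counted as an AE. The consequence is inflated AE rates and added noise in both arms. It is not evidence of bias between arms, and the C_max and AUC analyses and the sample size are untouched. This is a modest fault in a descriptive secondary analysis, worth correcting because the correction is nearly free.

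The number of participants affected cannot be estimated from the documents. A reader might multiply an assumed infection rate and duration by the 238 participants. The documents give neither input, and the product would ignore items 14, 18 and 27, the Day -1 review and the clinical-significance limit. It would be at best an upper bound on assumed inputs.

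The infection-at-entry point is secondary: an unexplained gap between the stated risk and the named criteria, not a direct contradiction. The conclusion assumes that 12.1 and 8.4.2 are applied as written and that no rule in the unseen table shells overrides them.

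**What to change.** - **Protocol 12.1.** Move the reference point of the exemption from the screening visit to dosing on Day 1. Keep the condition that the problem has not worsened, so that worsening after the dose still counts.
- **SAP 5.6.1.** Define the tabulated AEs as those with onset or worsening after dosing, and list conditions with pre-dose onset separately. Set this before unblinding.
- **Data capture.** Medical history is scheduled at screening, so say where a condition that begins after that visit is recorded; otherwise the separate listing may be incomplete.
- **Eligibility.** The sponsor and investigator should reconcile the warning in 2.2, the criteria in 5.4 and the Day -1 and Day 1 checks, and decide which clinical rule applies. They need to take account of 5.6, which bars rescreening of screen failures, and 6.6.2, which bars re-enrolment of a randomized participant who withdraws.

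The analysis change costs a few words in 12.1 and a sentence or two in the SAP, and uses an onset time that is already collected. The protocol edit has to be approved by or filed with the Ethics Committee under 10.2. One limit remains: with no safety laboratory sample between screening and Day 4 in the schedule, an abnormality first seen on Day 4 cannot be dated to before or after the dose, so the gain is mainly for symptoms and diagnoses.

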12.2 Further Details and Clarifications on the SAE Definition

Hospitalization is warranted or prolonged which will not be treated as SAEs in the following conditions:

- For diagnosis or elective surgery for the existing diseases;

- For efficacy assessment in the trial;
- For predefined course of treatment for the studied disease in the trial;
- For medical reimbursement consideration;
- Scheduled hospitalization outlined in the protocol;
- Hospitalization planned prior to the trial;
- For elective surgery not for an AE;
- For comprehensive medical examination.

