8.4 Adverse Events and Serious Adverse Events

8.4.1 Definitions of AE and SAE

Adverse Event (AE) – Any untoward medical occurrence in a clinical investigation participant administered a pharmaceutical product and that does not necessarily have a causal relationship with this treatment. An AE can therefore be any unfavorable and unintended sign (including an abnormal laboratory finding), symptom, or disease temporally associated with the use of a medicinal (investigational) product, whether or not related to the medicinal (investigational) product.

Serious Adverse Event (SAE) – Any untoward medical occurrence that at any dose:

- Results in death,
- Is life-threatening,
- Requires inpatient hospitalization or prolongation of existing hospitalization,
- Results in persistent or significant disability/incapacity, or
- Is a congenital anomaly/birth defect.

Suspected Unexpected Serious Adverse Reaction (SUSAR) – an adverse reaction that meets three criteria: suspected, unexpected and serious.

- Suspected: There is a reasonable possibility that the drug caused the adverse drug reaction.
- Unexpected: An adverse reaction, the nature or severity of which is not consistent with the applicable product information (e.g., the reference safety information).
- Serious: See above for SAE.

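### Protocol 12.2 removes SAE status from an admission to diagnose an existing disease even if that disease worsened after dosing, which conflicts with 12.1, 8.4.1 and SAP 5.6.1

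*Protocol*

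**What the plan says.** Four places in the documents bear on whether such an admission is serious.

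- **Protocol 12.2** opens with "Hospitalization is warranted or prolonged which will not be treated as SAEs in the following conditions". Its first item is "For diagnosis or elective surgery for the existing diseases". A later item in the same list is "For elective surgery not for an AE".
- **Protocol 12.1** leaves an AE unrecorded for "diseases or conditions or laboratory abnormalities that have been existing or detected prior to screening visit without further deterioration".
- **Protocol 8.4.1** gives five seriousness criteria, one of which is "Requires inpatient hospitalization or prolongation of existing hospitalization". It does not refer to 12.2. The SUSAR definition in the same section takes its seriousness limb from that list: "Serious: See above for SAE".
- **SAP 5.6.1** repeats the five criteria for analysis and carries over none of the 12.2 exemptions.

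Two other sections set the consequences. Protocol 8.4.6 requires the investigator to report an SAE to the sponsor at once, usually within 24 hours. Protocol 8.4.9 states that adverse events of special interest do not apply.

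**The concern.** Section 12.1 separates a stable pre-existing condition, which is not an AE, from one that has deteriorated, which is. One would expect 12.2 to draw the same line for hospitalization, but its first item does not. It exempts by the purpose of the admission and by the word existing, with no stability condition and no date by which the disease must have existed.

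What is at stake is the reporting class of a small group of events. Section 2.2 lists reactivation, exacerbation or worsening of underlying disease among the reference product's warnings; for heart failure it says "Worsening or new onset, may occur". An event that is not fatal, life-threatening, disabling or a congenital anomaly can become an SAE only through hospitalization, because 8.4.1 has no criterion for other medically important events. If 12.2 closes that route, 8.4.9 offers no second one. The event would still be recorded, graded and followed as an AE, but the 24-hour report depends on SAE status.

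**Working it through.** No arithmetic applies, because the point concerns definitions and the documents give no rate for such admissions. The check is to take a disease that existed before screening, assume it deteriorates after dosing, and read each section in turn.

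1. **Is it an AE?** Yes. Section 12.1 withholds AE status only while there is no deterioration.
2. **Is it serious?** Under 8.4.1 and SAP 5.6.1, yes, if it requires or prolongs an inpatient stay. Neither text qualifies this.
3. **Does 12.2 remove that status?** This depends on why the participant was admitted:

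| Admission or outcome | 8.4.1 and SAP 5.6.1 | 12.2 | Result |
|---|---|---|---|
| Diagnostic work-up of the worsened disease | Serious | Exempt (first item) | Direct conflict |
| Elective surgery because of the worsening | Serious | Exempt under the first item; the later item implies not exempt | Unclear within 12.2 |
| Treatment or other non-elective care | Serious | No item clearly applies | Remains an SAE |
| Event also fatal, life-threatening or disabling | Serious on another criterion | Addresses hospitalization only | Remains an SAE |

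4. **Which text prevails?** Neither document says. In the first row, one investigator could follow 8.4.1 and report while another could follow 12.2 and not report, and both would be within the protocol.
5. **What follows downstream?**
   - The 24-hour report in 8.4.6 applies only to an event classed as an SAE.
   - SUSAR seriousness refers back to the SAE definition, so expedited reporting is also exposed, but only if the event is suspected and unexpected as well.
   - Because the SAP omits the exemptions, an event not reported as an SAE under 12.2 would still meet the SAP's definition.

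The two elective-surgery items show that 12.2 can state an AE limit where one is wanted. No item places that limit on admission for diagnosis.

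**The case against.** The strongest reply is that 12.2 should be read with 12.1, which stands directly above it. Section 12.1 speaks of conditions present before screening and not deteriorating. If existing diseases in 12.2 carries that sense, both the date and the stability condition are supplied, and the later elective-surgery item suggests that AE-driven admissions were never meant to be exempt. This is a plausible account of the intent. It is not written, however, and a reporting rule should not depend on an inference.

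Other parts of the reply stand and limit the point.

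- **Population.** Section 5.3 requires no history of chronic or serious disease. Section 5.4 excludes hepatitis B surface antigen positivity, demyelinating disorders and heart failure or cardiac disease that may lead to it. What remains is minor, latent or undetected disease.
- **SUSARs.** The risks named in 2.2 come from the prescribing information, so they would usually be expected in nature. They would not be SUSARs unless unexpectedly severe, whatever 12.2 says. Section 8.4.8 also has the sponsor assess safety information whatever its source. That assessment starts only when the information arrives, and without a 24-hour report it may arrive through routine AE recording.

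A reader might infer more than the text supports:

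- That any worsened disease leading to admission escapes reporting. It does not: admission for treatment is not on the list.
- That a disease first arising after dosing is also exempt. The missing date makes this arguable, but it is a strained use of the word existing.
- That such diseases usually first present as a diagnostic admission. Nothing in either document says so.
- That one exempted event could halve the SAE count or reverse the difference between arms. Section 2.2 does report only two SAEs in the cited similarity study, but they were an angioedema in the biosimilar arm and a femoral neck fracture in the US reference arm. Neither is described as a worsened existing disease or a diagnostic admission, and one per arm gives no difference in counts to reverse. Safety is also summarized descriptively (Protocol 9.5), so no inferential result depends on it.

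**Conclusion.** The inconsistency is real and narrow. For a pre-existing disease that deteriorates after dosing and leads to admission for diagnosis, 12.1 with 8.4.1 and SAP 5.6.1 gives an SAE, and the first item of 12.2 says it is not one. For elective surgery prompted by the worsening, 12.2 is unclear within itself. The firmer loss is the 24-hour report. Loss of expedited reporting is possible only for an event that is also suspected and unexpected. An event may be classed differently for reporting and for analysis.

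The size cannot be given as a number and is probably small in this healthy population. The conclusion rests on reading 12.2 as written, without importing the 12.1 condition, and on neither document stating which section prevails. It does not touch the primary pharmacokinetic analysis. The change is still worth making, because the text can give the wrong seriousness class and correcting it takes little effort.

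**What to change.** In Protocol 12.2, limit the first item to diseases that existed before the reference point used in 12.1 (the screening visit) and have not deteriorated since. Using the dosing date here would create a second reference point: screening can precede dosing by up to 28 days, and the two sections would again disagree.

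Add one sentence to 12.2: none of its hospitalization exemptions applies when the admission is for an AE. This settles both the diagnostic and the elective-surgery cases and leaves the remaining items intact for admissions unrelated to an AE.

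In Protocol 8.4.1, add a cross-reference to 12.2. In SAP 5.6.1, use the same SAE definition, either by pointing to 8.4.1 and 12.2 or by repeating the revised exemptions, so that reporting and analysis classify each event alike.

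The cost is a minor amendment, which under Protocol 13.4 needs approval by the principal investigator, the sponsor and the ethics committee, with a matching SAP update. No procedure, visit or data item is added. The only running cost is possibly an occasional extra SAE report.
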